#### 6.5.4.4 Immune-related adverse events

Of note, if the AE is considered immune-related, both drugs in the combination should be delayed according to recommended dose modifications. If a participant experiences several irAEs, the most conservative recommendation should be followed.

The CTCAE V5.0 must be used to grade the severity of AEs.

When SAR444245 can be restarted, they should be administered at the initial planned dose and schedule as no modification is allowed:

- If the toxicity does not resolve or the criteria for resuming treatment are not met, the participant must be discontinued from all study drugs.
- If the toxicities do resolve, the combination of SAR444245 and cetuximab may be restarted at the discretion of the investigator.

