## **6.5 DOSE MODIFICATION**

### **6.5.1 General rules**

Dose modifications for SAR444245 and cetuximab are permitted according to the guidelines described in this section. Modification of dose levels in case of dose reduction for cetuximab is described in [Table 4](#).

Dose modifications different from those stated in the protocol should only be made in consultation with the Sponsor, unless required for immediate participant safety.

**Cycle delay** (ie, at Day 1 delay for all IMPs) or **dose omission** (ie, omission of any component of the IMP within a cycle) are permitted in case of treatment-emergent adverse event (TEAE). Dose modification will be made according to the worst grade of toxicity observed within a cycle. If a participant experiences several toxicities and there are conflicting recommendations, the most conservative recommended dose adjustment should be followed. Once a dose has been decreased, intra-patient re-escalation back to the previous dose level is not permitted.

Administration of the study treatment will be discontinued in the event of a TEAE that persists despite appropriate dose modifications or any other TEAE that, in the opinion of the Investigator, warrants discontinuation.

If any of the IMP components is permanently discontinued, the other IMP component can be continued until disease progression or other criteria as detailed in Section 7.1.1 of the master protocol are met. In this case it is partial permanent discontinuation and the end of treatment (EOT) assessment will be 30 days after the date of the last administration of the remaining IMP. When all IMP components are permanently discontinued it is full permanent discontinuation.

All changes to study treatment administration must be recorded in the electronic case report form (e-CRF).

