**Table 8 - Guidelines for the management of immune Cell-Associated Neurotoxicity Syndrome (ICANS)**

| Event severity
(ASTCT Consensus Grading criteria)   | Recommended SAR444245
dose modification and supportive care guidelines   |
|--|---|
| Mild
Grade 1
ICE score 7-9. Awakens spontaneously | No intervention required other than close clinical monitoring.   |
| Moderate
Grade 2
ICE score 3-6. Awakens to voice. | Delay SAR444245a.
Initiate treatment with IV corticosteroids should be initiated as needed. SAR444245 may be resumed only after participant recovery or improvement to Grade 1 after corticosteroid taper. Consideration for reduction of SAR444245 dose to ■ μg/kg as per Investigator with Sponsor consultation. |

| Event severity
(ASTCT Consensus Grading criteria)  | Recommended SAR444245
dose modification and supportive care guidelines   |
|---|---|
| Severe or Life-threatening  | If Grade 3 ICANS, delay SAR444245.  |
| Grade 3
ICE score 0-2. Awakens only to tactile stimulus.
Any clinical seizure focal or generalized that resolves rapidly or nonconvulsive seizures on EEG that resolve with intervention.   | When symptoms have resolved or improved to Grade 1 after corticosteroid taper, SAR444245 can be either restarted at $\blacksquare$ $\mu\text{g}/\text{kg}$ or permanently discontinued, as clinically indicated, and upon discussions between the Investigator and Sponsor.
Treatment with IV corticosteroids should be initiated. Concomitant CRS may require tocilizumab or alternative therapies per site practice in CRS management and should be handled as described in Table 7 .
Corticosteroids can then be administered IV or orally every 8 hours for up to 3 days, then tapered over 4 days.   |

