**Table 9 - Guidelines for the management of Vascular Leak Syndrome (VLS)**

| Event severity
(NCI-CTCAE V5.0)  | Recommended SAR444245
dose modification and supportive care guidelines   |
|---|---|
| Mild
Grade 1
Asymptomatic  | No intervention required other than clinical monitoring.  |
| Moderate
Grade 2
Symptomatic; medical intervention indicated   | Delay SAR444245. Upon resolution of VLS or improvement to Grade 1, SAR444245 a can be resumed at the reduced dose of ■ μg/kg

The initial strategy is to administer boluses of crystalloids with a goal of providing the minimum effective volume that optimizes blood pressure together with a fluid-restrictive strategy is advocated to limit interstitial fluid volume expansion.  |
| Severe or Life-threatening
Grade 3:
Severe symptoms; intervention indicated

Grade 4:
Life-threatening consequences;
urgent intervention indicated | If Grade 3 or Grade 4 VLS, permanently discontinue SAR444245.

In participants with severe shock, blood pressure may be only partially responsive or refractory to IV crystalloid fluids.

Severe or persistent hypotension is to be managed by the administration of vasopressors. A trial of 25% albumin IV is an additional option, although its efficacy is limited to those with a severe capillary leak. In those who remain with refractory shock in the setting of low filling pressures, high molecular weight starches such as hetastarch (MW 450 kDa) and pentastarch (MW 264 kDa) may be effective in expanding the intravascular volume. Supportive care with invasive and noninvasive ventilation as well as renal replacement may be necessary in severe cases. When available, disease-specific therapy should be initiated as soon as possible to facilitate recovery.

During the recovery phase from severe capillary leak, the endothelial injury resolves and the capillary leak becomes less important, resulting in stabilization of blood pressure, at which time fluid overload symptoms and signs may predominate (eg, pulmonary edema, pleural effusions, acute respiratory distress syndrome, systemic edema, ascites). Volume removal with loop diuretics is the first-line therapy in these patients. In those with marginal blood pressure and fluid overload, the combination of loop diuretics and 25% albumin IV may facilitate volume removal. Patients with AKI refractory to diuretics will require renal replacement. |

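### Cohort B2: the irAE restart rule returns SAR444245 to its starting dose, which for a participant already dose-reduced breaks the ban on re-escalation in Section 6.5.1

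*Protocol*

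**What the plan says.** All references are to Substudy 05 (Cohort B2) unless another substudy is named.

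- **Section 6.5.4.4, Immune-related adverse events:** "When SAR444245 can be restarted, they should be administered at the initial planned dose and schedule as no modification is allowed". The same section leaves the decision to restart to the investigator once the toxicity has resolved: "the combination of SAR444245 and cetuximab may be restarted at the discretion of the investigator".
- **Section 6.5.1, General rules:** "Dose modifications for SAR444245 and cetuximab are permitted according to the guidelines described in this section". It then adds: "Once a dose has been decreased, intra-patient re-escalation back to the previous dose level is not permitted".
- **Table 9, vascular leak syndrome (VLS), Grade 2:** after resolution or improvement to Grade 1, SAR444245 "can be resumed at the reduced dose of" a stated level, whose figure is masked.
- **Table 8, ICANS, Grade 2:** "Consideration for reduction of SAR444245 dose to" a masked level, decided by the investigator with the sponsor. At Grade 3 the drug is either restarted at a masked level or stopped.
- **Table 7, cytokine release syndrome (CRS), Grade 3:** the drug is either restarted at a masked level or stopped.
- **Section 6.5.3:** SAR444245 may be lowered where the protocol says so or after discussion with the sponsor, and the investigator has the last word on dosing.

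**The concern.** The irAE section fixes the restart dose of SAR444245 at the starting level. It does not say what happens to a participant who is no longer on that level. Taken at its word, it moves someone whose dose was cut for one toxicity back up to the full dose after a second one. That is the step Section 6.5.1 rules out.

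The stake is participant safety and the clarity of the site instruction for an investigational IL-2 product. It is not the estimation of response rate. A site that consults the section written for the event finds the wrong dose there for this participant, and has to go to another section to learn that it should not be used.

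**Working it through.** The plan gives no figure to reproduce and no arithmetic bears on the conflict. The check is to follow two kinds of participant through the rules.

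**Participant A: dose already lowered**

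1. Grade 2 VLS occurs. SAR444245 is delayed and then resumed at the lowered dose (Table 9). The figure is masked, but the table itself describes the dose as reduced, so the masking does not matter.
2. An irAE follows. Both drugs are delayed, and the irAE resolves.
3. The investigator decides to restart.
4. Under Section 6.5.4.4 the restart dose is the starting dose.
5. Under Section 6.5.1 this participant may not go back to the previous dose level.

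Steps 4 and 5 are incompatible. Section 6.5.1 carries no irAE exception, and Section 6.5.4.4 does not mention prior reductions. The same applies after a Grade 2 ICANS reduction. It also applies after Grade 3 ICANS or Grade 3 CRS where the masked restart level is, as it appears, a lower one.

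**Participant B: dose never lowered**

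1. An irAE occurs and resolves, and the investigator restarts.
2. Section 6.5.4.4 gives the starting dose, which is also the current dose. There is no re-escalation, so the ban in Section 6.5.1 is not touched.
3. What remains is the remark that no modification is allowed, set against the general permission in Section 6.5.1. That permission is tied to the guidelines in the same chapter, and Section 6.5.4.4 is one of them. The two can be read together: after an irAE, hold or stop rather than reduce.

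**Comparison with the sister substudies**

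- Section 6.5.4.4 in Cohorts A2 and B1 carries almost the same sentence, but about pembrolizumab. It fits there because Section 6.5.1 of each bars pembrolizumab dose reductions.
- Cohort B2 gives no pembrolizumab, and both of its drugs may be modified (Section 6.5.1; cetuximab levels in Table 4).
- The B2 sentence names one drug and continues in the plural, so it is also unclear whether cetuximab is meant.

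This pattern suggests that the sentence was adapted from the pembrolizumab text without being refitted. That is an inference; the documents do not state it.

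**Size of the group**

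Section 9.2 plans 40 core participants and, if the sponsor opens the expansion, 56 more: 40 + 56 = 96. The conflict reaches only those among them who were already reduced and who restart after an irAE. The protocol gives no rate for either event.

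**The case against.** The strongest defence has three parts.

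**The sentence may be deliberate.** The irAE tables of Cohorts A2 and B1 cover SAR444245 as well as pembrolizumab, and they only continue, withhold or discontinue; no row reduces SAR444245. A B2 rule against reducing for an irAE would match them. This stands for participant B. A reader might infer that Section 6.5.4.4 contradicts Section 6.5.1 on whether SAR444245 may be modified at all. The documents do not support that, because the permission in Section 6.5.1 is subject to the event-specific guidelines. At most there is a tension with Sections 6.5.1 and 6.5.3. The defence does not help participant A, for whom the starting dose is not the current dose.

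**Section 6.5.1 already resolves clashes.** It says: "If a participant experiences several toxicities and there are conflicting recommendations, the most conservative recommended dose adjustment should be followed". An earlier VLS and a later irAE can plausibly fall under this. It also says: "Dose modifications different from those stated in the protocol should only be made in consultation with the Sponsor, unless required for immediate participant safety". These clauses limit the practical risk. They work, however, only if the site sets aside the dose given in the irAE section.

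**Discretion protects the participant.** The investigator decides whether to restart (Section 6.5.4.4) and has the final say on dosing (Section 6.5.3). This too limits the risk. The discretion in Section 6.5.4.4 concerns whether to restart, while the disputed sentence sets the dose.

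**Conclusion.** The conflict is real but narrow. For a Cohort B2 participant whose SAR444245 dose has already been lowered, the restart dose in Section 6.5.4.4 cannot be reconciled with the ban on re-escalation in Section 6.5.1, and the pathway that leads there is one the protocol itself creates. For a participant never reduced, the sentence is workable.

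The conclusion rests on reading the irAE sentence literally and on Section 6.5.1 containing no exception, which it does not. It does not depend on the masked dose values, because Table 9 alone is enough.

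A reader might go further and infer that participants will in practice be re-escalated, or that the response rate results are compromised. Neither is supported. The most-conservative rule, sponsor consultation and investigator discretion all stand in the way of the first, and nothing in the protocol links this sentence to any statistical figure. The point should be corrected because the written dosing rule is wrong for these participants and putting it right costs almost nothing.

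**What to change.** Delete the sentence from Section 6.5.4.4 of Substudy 05, or replace it with: *When SAR444245 is restarted, it is given at the participant's current dose level and is not re-escalated (Section 6.5.1); cetuximab restarts per Section 6.5.2 and Table 4.*

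The replacement should go no further. Writing a new irAE-driven reduction of SAR444245 into this section would be a change of dosing policy that the irAE tables of Cohorts A2 and B1 do not contain. Any further reduction stays under Section 6.5.3.

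The cost is a one-sentence wording change in one substudy. Sample size, endpoints and analysis are unchanged.

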### 6.5.2 Cycle delay and dose omission

The treatment window is  $\pm 3$  days for each of the Q3W IMP administrations. The treatment window is  $\pm 1$  day for cetuximab administration on Day 8 and Day 15 of each cycle.

A cycle is deemed to have been delayed if the treatment is administered  $\geq 4$  days beyond the theoretical day of Q3W IMP administration. The participant may receive the next dose after recovery from the toxicity as described in [Section 6.5.3](#). After cycle delayed, such participants may be considered for treatment resumption once the toxicity resolves or improves to Grade 1 or baseline.

Participants may have cycle delay, or dose omission if toxicity occurs and the participant does not recover according to following rules:

- For Q3W IMP administration: If toxicity occurs and the participant does not recover on the day of planned administration; restart of study IMPs could occur only on the initiation of the subsequent cycle.
- For cetuximab Day 8 and Day 15 administration in each cycle: if toxicity occurs and the patient does not recover on the day of planned infusion or within the following 3 days, infusion may be omitted.
- In case of cycle delay or dose omissions for the recovery of toxicity, the following rules should be followed for restart or discontinuation of the treatment:
  - In case of a cycle delay up to 14 days or a dose omission, it is per Investigator's decision to restart the study treatment.

- After a cycle delay of >14 days and ≤84 days, or 2 to 4 consecutive dose omissions, it is per Investigator’s decision to restart the study treatment or the IMP that is omitted, if a clear benefit from treatment is observed and after consultation with the Sponsor.
  - The study treatment must be permanently discontinued if the cycle delay is longer than 84 days, or if the participant has more than 4 consecutive dose omissions.
  - For any delayed cetuximab treatment, do not repeat the initial dose of 400 mg/m^2. At the restart of cetuximab treatment, all subsequent infusions will be at the appropriate dose level according to [Table 4](#).

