### 6.5.3 General guidelines for the management of treatment-related adverse events

Participants who experience Grade ≥3 treatment-related adverse events (TRAEs) at any time of the study (including clinically significant Grade 3 laboratory abnormalities as defined in Section 10.3.1 of the master protocol) will be required to delay or omit the IMP, unless specified otherwise in the protocol, and with the exception of the TRAEs resolving within 5 days. After cycle delay or dose omission, such participants may be considered for treatment resumption once the TRAE resolves or improves to Grade 1 or baseline. Treatment resumption is at the discretion of the Investigator and Sponsor, if thought to be in the best interest of the participant, except when specified otherwise in this protocol, or if the event has required the IMP temporary interruption for more than 84 days from the last scheduled dose.

The delay or omission of treatment for Grade 2 events is left at the discretion of the Investigator unless otherwise specified in this protocol.

No delay/omission or dose modification is required for Grade 1 events.

Dose reduction for SAR444245 from ■ μg/kg to ■ μg/kg or another lower dose may be decided when specified in the protocol or following discussions with the Sponsor.

The final decision on dose modification and/or corrective therapy will be based on the Investigator’s judgment, in the best interest of the participant.

Recommended guidelines for the management of specific AEs including immune-related AEs (irAEs), cytokine release syndrome (CRS), vascular leak syndrome (VLS) and IRRs are presented in [Section 6.5.4](#).

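### Cohort B2 (substudy 05) orders SAR444245 restarted at the full planned dose after an immune-related event on the ground that no modification is allowed, which is untrue for this drug in B2 and breaks the no-re-escalation rule once a participant has been reduced

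*Protocol*

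**What the plan says.** All references are to Substudy 05 (Cohort B2) unless stated.

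- **Section 6.5.4.4**, on immune-related adverse events, first holds both drugs: "both drugs in the combination should be delayed according to recommended dose modifications". It then sets the restart dose: "When SAR444245 can be restarted, they should be administered at the initial planned dose and schedule as no modification is allowed". Two bullets follow. The first stops all study drugs if the toxicity persists or the resumption criteria are unmet. The second reads: "If the toxicities do resolve, the combination of SAR444245 and cetuximab may be restarted at the discretion of the investigator".
- **Section 6.5.1** gives two general rules: "Dose modifications for SAR444245 and cetuximab are permitted according to the guidelines described in this section", and "Once a dose has been decreased, intra-patient re-escalation back to the previous dose level is not permitted".
- **Section 6.5.3** says that a reduction of SAR444245 to a specified level (redacted) "or another lower dose may be decided when specified in the protocol or following discussions with the Sponsor". It names immune-related events among those managed under 6.5.4.
- **The Synopsis and Table 3** fix the planned SAR444245 dose at 24 µg/kg every 3 weeks.
- **Table 9** lets SAR444245 resume at a reduced dose after Grade 2 vascular leak syndrome. The value is redacted, but the word reduced is not.

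Section 6.5.4.4 of Substudy 02 (Cohort A2) and of Substudy 04 (Cohort B1) carries the same restart sentence with pembrolizumab as its subject. In both substudies, Section 6.5.1 rules out pembrolizumab dose reductions.

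**The concern.** The restart sentence does two things. It prescribes a dose, and it gives a reason for that dose. The reason is that SAR444245 cannot be modified, which is not how B2 treats the drug elsewhere. A site reading only the immune-related event section would conclude that a reduced-dose restart is unavailable.

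The more serious case is a participant whose SAR444245 has already been reduced for another toxicity. Taken literally, the sentence sends that participant back up to 24 µg/kg after an immune-related event, and 6.5.1 prohibits exactly that. Section 2.3.1.2 names more frequent or more severe immune-activation events as a risk of the SAR444245 and cetuximab combination, so restarting after such an event is a foreseeable situation. What is at stake is participant safety and consistent dosing across sites, not the response-rate analysis.

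**Working it through.** No plan figure is involved, so the check sets the rules side by side and asks what dose each one gives.

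**Inputs.** The planned dose is 24 µg/kg (Synopsis, Table 3). Let d be the reduced dose. Its value is redacted, but Table 9 calls it reduced, so d < 24.

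**Case 1: participant never reduced; one immune-related event that resolves.**
- Under 6.5.4.4 the restart dose is 24 µg/kg, with modification excluded.
- Under 6.5.3 a lower dose may be chosen after discussion with the Sponsor.
- Under 6.5.1 modification of SAR444245 is permitted within the guidelines of Section 6.5.

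A restart at 24 µg/kg satisfies all three. What fails is the stated reason and the bar it implies: 6.5.3 leaves open an option that 6.5.4.4 says does not exist.

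**Case 2: participant reduced to d after Grade 2 vascular leak syndrome, resumed at d, and later has an immune-related event that resolves.**
- Under 6.5.4.4 the restart dose must equal 24 µg/kg.
- Under 6.5.1 a return from d to the previous level is not allowed, so the dose may not be 24 µg/kg.

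No dose meets both. The redaction does not matter, because the contradiction needs only d < 24.

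**Where the sentence fits.** In A2 and B1 the same wording is applied to pembrolizumab. There the reason is true, because pembrolizumab may be interrupted or stopped but not reduced. B2 contains no pembrolizumab. In the B2 sentence a single drug is followed by a plural pronoun, which is consistent with text carried over from another substudy; that origin is an inference. Reading the pronoun as covering both drugs does not help, since B2 Table 4 provides two reduced dose levels for cetuximab.

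**The case against.** The best defence is that 6.5.4.4 is a specific rule within a general one. Section 6.5.1 permits modifications only as the guidelines of Section 6.5 describe, and 6.5.4.4 is one of those guidelines. Section 6.5.3 is also permissive about reductions. On this view a narrower rule for immune-related events is a choice, not an error. This has some force in Case 1. It does not make the stated reason true, and it does not reconcile the sentence with the no-re-escalation rule in Case 2.

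A second defence is that safeguards already exist. Section 6.5.1 allows departures in consultation with the Sponsor, or for immediate safety, and applies the most conservative adjustment when several toxicities give conflicting recommendations. Section 6.5.3 leaves the final decision to Investigator judgment. This stands, and it limits the practical effect. The most-conservative rule might cover Case 2, but it is not clear that it reaches a single new event in a participant reduced earlier.

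A reader might infer three stronger points, which the documents do not support.

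- **That 6.5.4.4 contradicts Tables 7, 8 and 9.** Cytokine release syndrome, neurotoxicity and vascular leak syndrome have their own sections, and their tables do not govern restart after an immune-related event. They show only that SAR444245 can be reduced in B2 and how a participant may come to be on a reduced dose.
- **That 6.5.4.4 replaces the resumption conditions.** For delays of more than 14 and up to 84 days, 6.5.2 allows restart "if a clear benefit from treatment is observed and after consultation with the Sponsor", with no clause yielding to other sections. In 6.5.3 the threshold is that "such participants may be considered for treatment resumption once the TRAE resolves or improves to Grade 1 or baseline"; the exception wording there belongs to the following sentence, on who decides. The first bullet of 6.5.4.4 itself keeps resumption criteria in force. The missing cross-reference is editorial.
- **That the size of the re-escalation can be stated.** The reduced level is redacted, so any percentage would rest on a guess.

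**Conclusion.** The point holds in a narrow form. One sentence of current B2 text gives a wrong reason for the SAR444245 restart dose and, for a participant already reduced, an instruction that cannot be followed together with 6.5.1. This rests on the ordinary meaning of the sentence and on Table 9 describing the resumed dose as reduced; it does not depend on any redacted value or on the master protocol.

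It would be too strong to say that B2 bars a reduced-dose restart outright, because Sponsor consultation and Investigator judgment keep that option available. No event rate is claimed. No sample size, decision rule or confidence interval is affected. The sentence should still be corrected: a dosing instruction should not need to be overridden to be safe, and it would apply to the 40 planned core-phase participants and, if the expansion opens, to about 40 + 56 = 96.

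**What to change.** In Substudy 05, Section 6.5.4.4, replace the restart sentence with: *SAR444245 may be restarted at the current or a reduced dose per 6.5.1 and 6.5.3; re-escalation after a reduction is not permitted.*

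Optionally, point the resumption criteria in the first bullet to 6.5.2 and 6.5.3 as they stand. This should not add Sponsor approval for every restart: 6.5.2 leaves a restart after a delay of up to 14 days to the Investigator, and a blanket requirement would be stricter than that.

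The cost is one sentence, plus one optional cross-reference, in the next amendment of substudy 05. No assessments, visits or analyses change.
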